#### **5. Study Population**

Blueprint is centered around the RCT portion of this pilot study. As such, the primary characteristics of the targeted study population will be those individuals who have been admitted to a hospital environment and are seriously ill due to respiratory failure or insufficiency (i.e., conditions that typically require respiratory support such as pneumonia, acute respiratory distress syndrome [ARDS], influenza, trauma, and post-op complications) or cardiac failure or insufficiency (i.e., conditions that require advanced cardiac support such

as septic shock, myocardial infarction, cardiogenic shock, and congestive heart failure). Additionally, given the world-wide pandemic of 2020, patients who experience a hospital admission due to COVID-19 and require respiratory and/or cardiac support will also be enrolled.

**Eligibility Criteria:** Patients who are deemed eligible for study participation will ultimately be those individuals who experience high levels of psychological distress (i.e., HADS total  $\geq 8$ ).

Specifically, patients enrolled into this pilot, RCT will meet the following criteria:

#### Inclusion Criteria (at the time of hospital admission)

1. Adult patient  $\geq 18$  years of age.
2. Managed in a hospital setting for  $\geq 24$  hours during the time inclusion criterion #3 is met.
3. Presence of acute cardiac or respiratory failure, defined as having  $\geq 1$  of the following:
  - a. Mechanical ventilation via endotracheal tube for  $\geq 4$  hours
  - b. Non-invasive ventilation (CPAP, BiPAP) for  $\geq 4$  hours in a 24-hour period provided for acute respiratory failure (not for obstructive sleep apnea or other stable use)
  - c. New supplemental oxygen requirement  $\geq 2$  liters per minute (or increase in baseline continuous oxygen)
  - d. Use of vasopressors for shock of any etiology (ie. isoproterenol, phenylephrine, norepinephrine, epinephrine, dopamine, and vasopressin)
  - e. Use of inotropes for shock of any etiology (ie. dobutamine and milrinone)
  - f. Use of pulmonary vasodilators (ie. flolan, treprostinil, etc.)
  - g. Use of aortic balloon pump or cardiac assist device for cardiogenic shock
  - h. Use of diuretic intravenous drip (ie. lasix)
4. Cognitive status intact, defined as:
  - a. No history of significant cognitive impairment (e.g., dementia) per electronic medical records
  - b. Absence of current, significant cognitive impairment ( $\geq 3$  errors on the Callahan cognitive status screen)
  - c. Decisional capacity present
5. Absence of severe and/or persistent serious mental illness that could disrupt study participation, as noted in the electronic medical record (EMR) or affirmed by clinical staff at the time of screening and approach for consent.  
Defined as any of the following:
  - a. Treatment for severe or unstable mental illness (e.g., psychosis, bipolar affective disorder, schizoaffective disorder, schizoid personality disorder, schizophrenia [as per medical record], hospitalization for any psychiatric disorder) within the 6 months preceding the current hospital admission
  - b. No endorsement of active suicidality at time of admission or informed consent
  - c. No active substance abuse at a severity that impairs ability to participate
6. English fluency

#### Exclusion Criteria (at the time of hospital admission)

1. Complex medical care expected soon after discharge (e.g., planned surgeries, transplantation evaluation, extensive travel needs for follow up care, disruptive chemotherapy/radiation regimen)
2. Unable to complete study procedures as determined by staff.
3. Lack of access to either reliable smartphone with cellular data plan or Wi-Fi.

### Inclusion Criteria (at the time of hospital discharge; at home)

1. Elevated baseline psychological distress symptoms, defined as HADS total score of  $\geq 8$  at the completion of survey 1 (T1).

### Exclusion Criteria (at the time of hospital discharge; at home)

1. Failure to randomize within 1 month after discharge from the hospital to home.
2. Failure to access app within 1 month after randomization.

## 7. Study Procedures

### Screening, Recruitment and Consent

Screening for eligible patients will occur daily via MaestroCare by delegated study team members for the Aim 2 (RCT). For Aim 1 (usability), the study team will recruit healthy volunteers from the Pulmonary Medicine Healthy Volunteer Data Repository (Pro00102890). The study team will maintain a robust screening log of all individuals reviewed and will document whether or not each individual was eligible for the study. Additionally, they will document if each individual was approached for consent and the outcome of consent. It will be essential, for the future RCT that it is understood why individuals are or are not eligible for approach and/or subsequent consent, therefore the screening log will track reason for ineligibility and reason for non-consent.

For those individuals who are eligible to consent, the study team will recruit the individual in-person or remotely using an approved telephone script. Patients for the RCT will be approached, ideally at the time of their hospital admission, just prior to their discharge to an in home setting, if possible. Should the study team be unable to make contact with the patient during the hospitalization, the study team will contact them once discharged home. However, patients can be approached earlier in their admission, if well enough, or within a week of returning to their home for participation in the study. All patients will be informed at the time of recruitment that research is voluntary and they do not have to participate if they do not want to. Furthermore, they will be informed that participation will not affect their care in any way. If a patient chooses to not participate, he/she will be documented as a 'declined' patient and the date of decline, as well as reason for decline (if available) will be documented. Should a patient be approached while in the hospital and opt to consent, they will be asked to complete the app registration and baseline survey, and then a study team member will contact them, once home, to remind them to login to the app to complete T1 for randomization. Should a patient be approached post-hospital discharge, he/she will be asked to complete app registration, baseline survey and T1 on the same day for study enrollment and randomization purposes. As with screening, the study team will be required to maintain a robust enrollment log that documents the patient's consent status, version of informed consent with reference date of IRB approval, and then ultimate study status with associated visit milestones.

It is important to note that for this study, there are several statuses an individual can have. They are listed below:

- **Screened (in screening or screened):** defined as any individual whose EMR (aim 2 only) or REDCap CRF (aim 1 only) has been reviewed against protocol for eligibility purposes. Individuals who are assigned this status must be noted on the screening log.
- **Consented:** defined as any individual who is approached for consent and voluntarily chooses to consent to the study, the procedures, risks and benefits with the understanding that they may withdraw at any time. A signed/dated informed consent must be on record to account for this individual. Patients, enrolled in the aim 2, who reach this status will be required to complete T1 at the time of hospital discharge within 1 week but no more than 1 month from returning to home. Individuals who are assigned this status must be noted on the enrollment log.

- **Declined:** defined as any individual who was approached for consent, but opted to NOT consent and therefore to NOT participate in the study. Individuals who are assigned this status must be noted on the screening log.
- **Randomized (aim 2 only):** defined as any patient who was consented to the study, is discharged from hospital to home, completes T1 survey, and continues to meet all eligibility criteria (see Eligibility Criteria, section 5). Patients who reach this status will be required to interact with the app on a daily basis for 1 month and then complete T2 and T3. Patients who are assigned this status must be maintained on the enrollment log.
- **Screen Failed (aim 2 only):** defined as any patient who was consented to the study, is discharged from hospital to home, and completes T1 survey, and DOES NOT meet all eligibility criteria (see Eligibility Criteria, section 5). Patients who reach this status have no additional follow-ups or study requirements. Patients who are assigned this status must be maintained on the enrollment log.
- **Withdraw by PI or Self:** defined as any individual who voluntarily consents to participate in the study, but is then withdrawn from the study. The PI may withdraw a participant at any time without their consent if the PI deems it is in their best interest to no longer participate OR the patient demonstrates continuous lack of compliance with study protocol and study procedures. Additionally, if the patient is re-admitted to the hospital during the time of randomization, he/she will be withdrawn from the study by the PI. The study team may re-enroll the patient at the time of discharge following the same screening procedures. The patient may withdraw themselves at any time; the study team will be asked to document the reason for withdraw for study records. Patients who reach this status have no additional follow-ups or study requirements. Patients who are assigned this status must be maintained on the enrollment log.
- **Lost to Follow-Up (LTF):** defined as any individual who voluntarily consents to participate in the study but after non-compliance and at least 3 documented, attempted contacts appropriately spaced 1-5 days apart, the individual will be considered LTF.
  - For aim 2 only:
    - Patients who reach this status have no additional follow-ups or study requirements. Patients who are assigned this status must be maintained on the enrollment log.
    - A patient who returns the study team's contacts within 1 week of last attempted contact may resume study participation.
- **Completed:** defined as any individual who both consented and randomized to the study and completed T1-T3 (aim 2 only) or any individual who completed assigned study visit (aim 1 only). Individuals who reach this status have no additional follow-up or study requirements. Individuals who are assigned this status must be maintained on the enrollment log.

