#### **4. Study Objectives, Hypotheses, and Outcomes**

The overall objective of the pilot RCT is to determine the feasibility, acceptability and clinical impact of the intervention on patients' 1- and 3-month psychological distress symptoms of a self-directed mobile coping skills training (mCST) intervention, known as "Blueprint" as compared to usual care control.

The primary hypothesis in which this study is based is that the mCST will be feasible and acceptable based on comparison of observed to priori benchmarks.

The second hypothesis is compared to usual care, the mCST use by enrolled subjects will lead to improvement in symptoms of psychological distress via the HADS and PTSS at the 1- and 3-month mark post randomization.

The primary outcome of the pilot RCT is centered on acceptability and feasibility. The Client Satisfaction Questionnaire 8 will measure acceptability with open-ended participant feedback completed at the time of T3, which is considered end of study (EOS). Feasibility will be measured by frequency of randomization, retention, and adherence. Secondary outcomes are HADS and PTSS scores at 1 and 3 months post-randomization.

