#### Adverse events (AEs), serious adverse events, (SAEs) and unanticipated problems (UPs).

It is recognized that there is a slight risk that some participants may become distressed when completing self-report measures or participating in interviews. When necessary, participants who experience psychological distress *related to completing questionnaires* will be referred for appropriate psychiatric or psychological care. All participants will have access to the PI’s contact information 24 hours a day (shown in the consent form). If a telephone interview is required, a trained study team member who has been trained to be sensitive to the nature of these issues will conduct it.

It is anticipated, in this study, for AEs to be extremely rare as it is a behavioral study. However, it is possible that participants could become distressed in a hospital setting or post-discharge due to increased illness and/or limitations. As such, participants could exhibit signs of and/or experience suicidal ideations or be admitted for mental health symptoms. Therefore, for this study, only increased levels of distress related to completing the questionnaires or completing the coping skills practice and/or suicidal ideations will be considered AEs.

Like, AEs, it is not anticipated that SAEs will occur. However, for this study, an SAE would be defined as a suicide attempt, a hospitalization (post hospitalization that initiated the patient’s eligibility for study

participation), or death. All serious adverse events will be reported within the standard timelines required to the IRB, study sponsor, and/or DSMB, as appropriate and when applicable.

Given the nature of this study, it is anticipated that most enrolled patients will not complete their study visits within the assigned protocol window. Additionally, it is expected that visits and/or mCST practices will be missed. As such, these will not be considered protocol deviations. Should other protocol deviations or unanticipated problems occur, they will be discussed with the PI, documented, and reported to the IRB, study sponsor, and/or DSMB, as appropriate and when applicable.

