2.2 Exclusion Criteria

Patients were excluded from Blueprint if they satisfied the following exclusion criteria:

At time of hospital admission:

- Complex medical care expected soon after discharge (e.g., planned surgeries, transplantation evaluation, extensive travel needs for follow up care, disruptive chemotherapy/radiation regimen)
- Unable to complete study procedures as determined by staff.
- Lack of access to either reliable smartphone with cellular data plan or wifi

At time of hospital discharge:

- Failure to randomize within 1 month after discharge from the hospital to home.
- Failure to access app within 1 month after randomization.

The following additional exclusion criteria were applied after data collection:

- Any data recorded after a participant has withdrawn

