3.1 Primary Outcome(s)

Variable	Dataset	Description	Specifications

hads	Blueprint/Baseline	HADS total score at T0	Continuous
Hads	Blueprint/T1	HADS total score at T1	Continuous (may need to be derived from item scores HADS01—HADS14)
Score_hads	Blueprint/T2	HADS total score at T2	Continuous (may need to be derived from item scores HADS01—HADS14)
Score_hads	Blueprint/T3	HADS total score at T3	Continuous (may need to be derived from item scores HADS01—HADS14)
ptss	Blueprint/T1	PTSS total score at T1	Continuous (may need to be derived from item scores ptss_1—ptss_10)
Score_ptss	Blueprint/T2	PTSS total score at T2	Continuous (may need to be derived from item scores ptss_1—ptss_10)
Score_ptss	Blueprint/T3	PTSS total score at T3	Continuous (may need to be derived from item scores ptss_1—ptss_10)
D3mo_HADS	Blueprint/T3 Blueprint/T1	Change in HADS at 3 months	Derived as Score_hads(T3) - ???
D1mo_HADS	Blueprint/T2 Blueprint/T1	Change in HADS at 1 months	Derived as Score_hads(T2) - ???
D3mo_PTSS	Blueprint/T3 Blueprint/T1	Change in PTSS at 3 months	Derived as Score_ptss(T3) - ???
D1mo_PTSS	Blueprint/T2 Blueprint/T1	Change in PTSS at 1 months	Derived as Score_ptss(T2) - ???
ADLs/IADLs	T1, t2, t3		Not really an outcome but...
Systems Usability Scale	T1		
PHQ-10 physical symptom scale	T1, t2, t3		
Quality of life 100-point VAS	T1, t2, t3		
List		Feasibility	
Eligibility: 70% of positive screens Consent: 80% of eligible Randomized: 80% of consented Retention: 80% Adherence: 75% of tasks
 
***note that these need to be defined a bit more specifically

CSQ-8	`	Acceptability	

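### The PI may withdraw non-compliant patients and end their follow-up, although adherence and retention are primary feasibility outcomes and only the app arms have daily practice to miss

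*Protocol*

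**What the plan says.** Protocol section 7 (Screening, Recruitment and Consent) lists the statuses a patient can have. Under withdrawal by PI or self, the PI may remove a patient at any time without consent on either of two grounds: the patient's best interest, or that "the patient demonstrates continuous lack of compliance with study protocol and study procedures". No threshold, period or arm-specific meaning is given for the second ground. The consequence is stated: "Patients who reach this status have no additional follow-ups or study requirements".

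Section 4 makes the same behaviour part of the primary outcome: "Feasibility will be measured by frequency of randomization, retention, and adherence". SAP section 3.1 sets the benchmarks, "Retention: 80% Adherence: 75% of tasks", and adds a reminder: "note that these need to be defined a bit more specifically".

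In protocol section 12, the part on adverse events says that "it is expected that visits and/or mCST practices will be missed" and that such misses are not protocol deviations. SAP section 2.2 excludes from analysis "Any data recorded after a participant has withdrawn".

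Protocol section 3 asks Arms 1 and 2 to use the app for 28 days and gives the study team a dashboard showing each patient's use. Arm 3 receives neither app nor therapist and owes only surveys.

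**The concern.** A feasibility pilot should observe patients who stop using the app, because they are part of what it is meant to measure. Here one behaviour is a primary outcome, an expected event and a ground for ending observation. The decision is discretionary. Nothing in the protocol blinds the PI to arm, and app use is visible on the dashboard.

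Three results are exposed. Retention falls by PI action as well as by patients' own choice. Outstanding HADS, PTSS and CSQ-8 data are lost because of behaviour after randomisation. The adherence estimate depends on how a withdrawn patient's remaining tasks are counted. The pilot is meant to inform a definitive trial, so errors in these estimates would carry into that design, and surveys never requested cannot be recovered in analysis.

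**Working it through.** The plan gives no figure to reproduce. Steps 1 and 2 compare the texts. Steps 3 to 5 are illustrations with assumed inputs.

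**1. Whom the ground reaches.** The same status list has a lost-to-follow-up status for non-compliant patients after at least three failed contacts. What the PI ground adds is therefore mainly patients who can still be reached, or who have not yet had three attempts. Its wording covers all arms, and controls can miss the weekly HADS, T2 or T3. Only Arms 1 and 2 have app practice to miss, and only while it is required: section 10 makes app use optional between T2 and T3. The difference between arms is therefore confined to about the first month.

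**2. What is certainly lost.** Any survey still due. If T2 is counted from randomisation, as the Study Visits text has it, a withdrawal during the 28 days of app use loses both T2 and T3. Sections 3 and 4 place the CSQ-8 at T3, while the forms in Appendix 3 carry its items in the T2 survey. A patient withdrawn before T2 never completes it in either case.

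**3. Retention.** Let w be the share of app patients withdrawn on this ground (assumed). With all randomised app patients as denominator, retention is at most 1 − w.
- Protocol numbers: 25 + 25 = 50 app patients. At w = 20%, 10 are withdrawn and retention is at most 40/50 = 80%.
- SAP numbers: 15 + 15 = 30 app patients. At w = 20%, 6 are withdrawn and retention is at most 24/30 = 80%.
- For w from 5% to 30%, the ceiling runs from 95% to 70%.

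**4. Adherence.** Assume a share q of app patients do 60% of tasks for 14 days and then stop, while the rest do 80% throughout. Assume equal tasks each day. A stopper completes 0.60 × 14 = 8.4 of 28 task-days, or 30%.
- All scheduled tasks counted: 0.80(1 − q) + 0.30q. This is 70% at q = 0.2 and 65% at q = 0.3.
- Tasks counted only up to withdrawal on day d, averaging patients' rates: 0.80(1 − q) + q × 8.4/d.
- The same, pooling tasks: [0.80 × 28(1 − q) + 8.4q] / [28(1 − q) + qd]. For q = 0.2 this is 19.6/(22.4 + 0.2d); for q = 0.3 it is 18.2/(19.6 + 0.3d).

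| Withdrawal day d | q = 0.2, patient average | q = 0.2, pooled | q = 0.3, patient average | q = 0.3, pooled |
|---|---|---|---|---|
| 14 | 76.0% | 77.8% | 74.0% | 76.5% |
| 16 | 74.5% | 76.6% | 71.8% | 74.6% |
| 21 | 72.0% | 73.7% | 68.0% | 70.3% |
| 28 (nothing cut) | 70.0% | 70.0% | 65.0% | 65.0% |

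The cut-off always raises the figure. Whether it passes 75% depends on the withdrawal day and the averaging rule. At q = 0.2 the pooled figure is below 75% from day 19 (19.6/26.2 = 74.8%).

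As an outer bound, suppose withdrawn patients left the calculation altogether and the rest stood exactly at 75%. With withdrawn patients at 0 to 40% of tasks (a), adherence over all randomised app patients would be wa + (1 − w) × 75%. That gives 67.5–71.5% at w = 10%, 60–68% at 20% and 52.5–64.5% at 30%. SAP 2.2 does not prescribe that removal.

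**5. HADS and PTSS.** If outcomes of a share w of app patients are lost and these patients would have differed from the rest by g SD, a simple mean of those remaining shifts by w × g, with no control withdrawn. At w = 20%, the shift is 0.20 × 0.5 = 0.10 SD for g = 0.5. It is 0.05 SD for g = 0.25 and 0.20 SD for g = 1.0. Against the SAP's yardstick of half a baseline SD, these are 20%, 10% and 40%. The sign follows g, which the documents do not give.

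**The case against.** The strongest reply is that the plan does not say adherence will be inflated. SAP 2.2 removes only data recorded after withdrawal and is silent on scheduled tasks. SAP 3.1 admits that the benchmarks are unfinished. The one adherence-type row in SAP Table 2, the share completing every intervention component, sits under arm-level totals, where an early withdrawal would count as not completing. All of this stands: inflation is possible, not established. A reader might infer from the 76% above that the rule turns a failed benchmark into a met one. That needs withdrawal close to the day use stops, which hardly fits the wording of the ground, and section 3 lets staff remind the patient first.

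A reader might also infer that the control arm stays complete and the comparison tilts towards mCST. The documents support neither. Controls can be withdrawn for missed surveys, and no passage says that patients who stop do worse. The planned mixed model still uses withdrawn patients' earlier scores, and the protocol disclaims a test of efficacy. Nor does the app-arm asymmetry run to T3, since app use is optional after T2.

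There are safeguards. Withdrawn patients stay on the enrolment log, a CONSORT diagram and retention by arm are planned, and the DSMB reviews dropout. Describing missed practice as expected also weighs against frequent use of the ground. These make withdrawals visible, but they do not bring back T2 and T3 data that were never requested.

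**Conclusion.** The concern holds in a limited form. It is certain that a patient withdrawn on this ground gives no further T2 or T3 data. With all randomised patients as denominator, that patient also counts against retention. The loss is likely, but not certain, to be heavier in Arms 1 and 2, and only during the first month. How often the ground would be used, and the direction of any bias in HADS or PTSS, cannot be known from the documents. Overstated adherence is a further possibility that the SAP leaves open. The percentages shown rest on assumed shares, task rates and withdrawal days, and only illustrate the scale. This is a stated rule that works against the trial's own primary outcome, and not merely a missing detail.

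**What to change.** **Protocol.** Delete non-compliance as a ground for PI withdrawal of randomised patients. State that a patient who stops using the app is still asked for the weekly HADS, T2 and T3 unless they decline. Leave the best-interest, readmission, suicidality and lost-to-follow-up provisions as they are; this change should not override them.

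**SAP.** Compute adherence over all tasks scheduled in the 28 days for every patient randomised to Arm 1 or 2, counting undone tasks as not done whatever the later status. Compute retention over all randomised patients, by arm. This also supplies part of the definition that SAP 3.1 says is needed. Read SAP 2.2 alongside it, including the separate exclusion for not opening the app within a month of randomisation, so that the denominators agree.

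**Cost.** One clause removed, one protocol sentence and two SAP sentences added. Observed adherence may look less favourable, and staff will keep inviting non-users to surveys.

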  - A native app that uses this downloaded as a self-contained program and is subject to the device operating system. The mCST created for this study known as "Blueprint", was developed, and is maintained by Pattern Health ([name]).
- Patient Health Questionnaire-10 (PHQ-10)
  - Physical symptoms
- Post-Traumatic Stress Scale survey (PTSS)
  - PTSD symptoms

- **Protocol Deviation (PD)**
  - An inadvertent event or event this is out of the control of the study team and/or the subject that occurs outside of the study protocol design and/or procedures.
- **Protocol Violation**
  - An act of intentionality that is committed by the study team and/or the subject that occurs outside of the study protocol design and/or procedures.
- **Serious Adverse Event (SAE)**
  - Defined as an adverse event that is both serious and expected in nature; the event may have a reasonable possibility that it is related to a study. SAEs for this study are defined as a suicide attempt, a hospitalization, or death.
- **Suicide Ideation (SI)**
  - The idea of committing self-harm and/or the intent to act on the idea of committing self-harm.
- **Unanticipated Problem (UP)**
  - Any other event, not meeting the definition of PD, UP, AE or SAE that, in the opinion of the principal investigator, merits documentation as it occurred outside the expected design of the study and/or study procedures. These events, like PDs, UPs, AEs, or SAEs, may be reported to the IRB and/or the study sponsor, as applicable.

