**CLICK NEXT TO SAVE YOUR RESULT**

#### [H. T2 Survey](#)

# T2

Second Survey

1. In the past month, have you been treated for depression, anxiety, PTSD, or any other psychiatric condition?

Response is \*\*Yes\*\* or \*\*No\*\*.

2. In the past month, have you been treated for depression or depressed mood?

Response is \*\*Yes\*\* or \*\*No\*\*.

3. Were you treated with medication?

Response is \*\*Yes\*\* or \*\*No\*\*.

4. Were you treated by a psychiatrist, psychologist, or counselor?

Response is \*\*Yes\*\* or \*\*No\*\*.

5. In the past month, have you been treated for anxiety?

Response is \*\*Yes\*\* or \*\*No\*\*.

6. Were you treated with medication?

Response is \*\*Yes\*\* or \*\*No\*\*.

7. Were you treated by a psychiatrist, psychologist, or counselor?

Response is \*\*Yes\*\* or \*\*No\*\*.

8. In the past month, have you been treated for post-traumatic stress disorder (PTSD)?

Response is \*\*Yes\*\* or \*\*No\*\*.

9. Were you treated with medication?

Response is \*\*Yes\*\* or \*\*No\*\*.

10. Were you treated by a psychiatrist, psychologist, or counselor?

Response is \*\*Yes\*\* or \*\*No\*\*.

11. In the past month, have you been treated for chronic pain?

Response is \*\*Yes\*\* or \*\*No\*\*.

12. Were you treated with medication?

Response is \*\*Yes\*\* or \*\*No\*\*.

13. Were you treated by a psychiatrist, psychologist, or counselor?

Response is \*\*Yes\*\* or \*\*No\*\*.

14. Since you were last discharged from the hospital, have you been admitted to the hospital again?

Response is \*\*Yes\*\* or \*\*No\*\*.

15. How many times have you been admitted?

Response is \*\*one\*\* of:

- Once
- 2 times
- 3 or more times

16. For the next questions, select the option that best fits your current situation.

(This is an information screen that requires no response)

Click Next to continue.

17. I have someone to confide in or talk to about myself and my problems.

Response is \*\*one\*\* of:

- Never
- Rarely
- Sometimes
- Usually
- Always

18. At the end of an average month, what describes how you usually feel when you are paying the bills?

Response is \*\*one\*\* of:

- Short on money and need more to pay bills
- Barely have enough to pay bills and for basic needs
- Have enough for just a few extra things
- Completely comfortable

19. Please select the response that describes how you felt in the past week.

(This is an information screen that requires no response)

Click Next to continue

20. I feel tense or wound up

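### The rule withdrawing readmitted patients does not say what period it covers; read as applying after allocation, it can discard randomised outcomes and let one person be allocated twice

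*Protocol*

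**What the plan says.** The list of participant statuses in protocol section 7 (Screening, Recruitment and Consent) includes a withdrawal status. Under it, "if the patient is re-admitted to the hospital during the time of randomization, he/she will be withdrawn from the study by the PI". The next sentence adds: "The study team may re-enroll the patient at the time of discharge following the same screening procedures". For anyone given this status, "Patients who reach this status have no additional follow-ups or study requirements". SAP 2.2 lists one further exclusion, applied after data collection: "Any data recorded after a participant has withdrawn".

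Four other places bear on how the rule is read:

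- **Randomized status (protocol section 7).** It begins once T1 is completed at home and eligibility is confirmed. "Patients who reach this status will be required to interact with the app on a daily basis for 1 month", and T2 and T3 follow.
- **Exclusion criteria at discharge (protocol section 5).** One ground is "Failure to randomize within 1 month after discharge from the hospital to home", so up to a month can pass between discharge and allocation.
- **T2 survey, items 14 and 15 (Appendix 3).** Item 14 asks "Since you were last discharged from the hospital, have you been admitted to the hospital again", and item 15 asks how many times. The T3 survey repeats both; the T1 survey has neither.
- **SAP 3.1.** The retention benchmark is 80%, with a note that the feasibility measures still need more specific definitions.

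**The concern.** Withdrawal under this rule is mandatory, but the period that triggers it is not defined. Two coordinators could treat the same readmitted patient differently, and both could claim to follow the protocol.

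Under the wider reading, three things are at stake:

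- A randomised patient's later distress scores are not collected, or are discarded, because of an event after allocation that may be related to the outcome.
- An illness event can be scored as a retention failure, and retention is part of the primary feasibility outcome.
- The re-enrolment sentence opens a path to a second T1 and a second allocation. The plan does not say whether the first arm is kept, how often a person may be randomised, or which enrolment is analysed.

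**Working it through.** The sample size is pragmatic and has no power calculation to reproduce. The check is therefore a comparison of the texts, followed by arithmetic on assumed rates.

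**1. Which period does the rule cover?**

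| Reading | Support | Consequence |
|---|---|---|
| Narrow: up to allocation | Allocation may come as late as a month after discharge. Elsewhere the protocol mostly treats randomisation as a point in time, for example when it counts outcomes from it (section 4). T2 and T3 ask randomised patients about readmission. | No randomised outcome is lost and no one carries app exposure into a second allocation. |
| Wide: the randomised period | Randomized is a status that runs through app use, T2 and T3. Allocation follows a survey completed at home, so taken literally it is a moment that can hardly contain a readmission. | Surveys due after the readmission are lost. Re-enrolment could follow exposure to the app. |

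Nothing in either document chooses between them.

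**2. Which outcomes go, under the wide reading?** SAP 2.2 removes only what is recorded after withdrawal. Readmission before T2 loses T2 and T3. Readmission between T2 and T3 loses T3 only; T1 and T2 still enter the PROC MIXED model.

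**3. How many patients?** The documents give no readmission rate. Assume r = 10%, 20% or 30%.

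- Protocol, N = 60: 60 × r = 6, 12 or 18.
- SAP, N = 45: 45 × r = 4.5, 9 or 13.5.

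**4. Precision, under the wide reading.** Take an unadjusted comparison of pooled app arms with control, in SD units, at a time point where every readmitted patient is missing. The 95% half-width is t(0.975, n1 + n2 − 2) × √(1/n1 + 1/n2).

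- 50 vs 10, no loss: 2.002 × √(1/50 + 1/10) = 0.69.
- 20% lost, 40 vs 8: 2.013 × √(1/40 + 1/8) = 0.78.
- 30% lost, 35 vs 7: 2.021 × √(1/35 + 1/7) = 0.84.
- SAP sizes, 30 vs 15: 0.64 with no loss and 0.72 at 20%.

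**5. Bias, under the wide reading.** Suppose readmitted patients score d SD worse, and there is no app effect within the readmitted or within the non-readmitted. Leaving the readmitted out shifts the app-minus-control difference by d × (r_control − r_app).

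- d = 1, r_app = 10%, r_control = 30%: 1 × (0.30 − 0.10) = 0.2 SD, against the SAP 4.2 yardstick of 0.5 baseline SD.
- Equal rates in the arms: 0.

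**6. A second allocation.** Re-enrolment by the same screening procedures leads to a new T1 and, if HADS is at least 8, to randomisation. If a person were allocated afresh, the chance of control would be about 10/60 = 1/6 (25:25:10), 2/8 = 1/4 (3:3:2) or 1/3 (1:1:1). These are approximate, because the SAP describes minimisation. One such person would be 1/10 = 10% or 1/15 = 6.7% of the control arm. I give no expected number, because no link in the chain has a documented probability.

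SAP 2.2 does not settle how a second enrolment is analysed. Applied by person, it deletes all the second enrolment's data. Applied by enrolment, one person counts twice.

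**The case against.** The strongest reply is that the narrow reading is natural and does no harm. The protocol mostly uses randomisation for a single event, a readmission rule makes sense for the gap of up to a month before it, and the T2 and T3 readmission items expect readmitted patients to be in follow-up. This stands as far as it goes: the text does not establish the wide reading. It does not exclude it either, and a mandatory rule should not depend on a guess.

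A reader might infer several stronger claims that the documents do not support:

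- **That readmitted patients will be randomised again.** Re-enrolment is optional. The person must pass screening again and again score at least 8 on HADS. No text says whether a new arm is then drawn.
- **That retention is capped at some figure.** That needs a readmission rate and a definition of retention, and neither is given. A person who re-enrols and completes might be counted as retained.
- **That both follow-up scores are always lost.** A readmission after T2 loses T3 only.
- **That recording hospitalisation as an SAE contradicts withdrawal.** The definitions state "SAEs for this study are defined as a suicide attempt, a hospitalization, or death", but an event can be recorded and the patient then withdrawn. Protocol section 12 already requires SAE recording, up to 30 days after participation ends.
- **That the arm comparison is necessarily biased.** In the simple model above, equal readmission rates give no shift, and nothing in the documents says the rates differ.

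It can also be said that this pilot does not test efficacy. That lowers the stakes for the distress comparison. It does not remove the effect on retention, which belongs to the primary outcome, or on the interval estimates that are the stated secondary goal.

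**Conclusion.** The point holds as an ambiguity with a damaging reading, not as a demonstrated loss. What is certain is the text: a mandatory withdrawal with an undefined trigger period, no follow-up afterwards, permitted re-enrolment without an allocation or counting rule, and an SAP that drops later data. What is conditional is the harm. If the rule covers the window before allocation, there is none. If it covers the randomised period, T2 and/or T3 distress scores are lost for a reason plausibly related to illness, the loss can count against the 80% retention benchmark, a person could be allocated and counted twice, and the rule conflicts with the T2 and T3 readmission items.

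The size is unknown. The 6 to 18 of 60 rests wholly on an assumed 10% to 30% readmission rate. The precision figures also assume that every readmitted patient is missing at the time point. The link between readmission and distress is plausible, but the documents do not measure it. Confidence is moderate.

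**What to change.** Reconcile the withdrawal rule with the Randomized status, the T2 and T3 readmission items and SAP 2.2:

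1. Limit the withdraw-and-rescreen sentences to readmission after consent but before randomisation.
2. State that a patient readmitted after randomisation continues T2 and T3 outcome collection on the original dates and is analysed in the assigned arm. Whether app use continues during or after the readmission stays with the investigators.
3. Allow one randomisation per person, checked at enrolment.
4. Say in SAP 2.2 that readmission after randomisation is not in itself a withdrawal.

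The SAP describes randomisation in the past tense. If the rule has already been applied to randomised patients, the SAP should therefore also report how many by arm, and which enrolment is analysed for anyone enrolled twice.

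The cost is a revised protocol rule, one SAP clarification and one check in the app or enrolment log. The downside is small: a few surveys may be answered during or soon after a readmission.

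An optional minor change is to anchor survey item 14 to the index hospital stay. Read literally, its reference point moves with each new discharge, so a patient readmitted once and home again could answer no.
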